Global Lomitapide Pregnancy Exposure Registry

Protocol Number: AEGR- 733-027

Version / Date Draft Protocol: Version 3.0 / 21 Nov 2013

Name of Test Drug: Lomitapide

US: NDA 203858

EU: MAA EMEA/H/C/002578/0000

Indication: Adult patients with Homozygous Familial Hypercholesterolaemia

(HoFH)

Sponsor: Aegerion Pharmaceuticals, Inc.

[name]

[name]

Responsible Medical Officer: [name]

VP Medical Affairs, EMEA [contact]

[contact]

Confidentiality Statement

The information contained herein is confidential and the proprietary property of Aegerion Pharmaceuticals, Inc. and any unauthorized use or disclosure of such information without the prior written authorization of Aegerion is expressly prohibited.

Confidential Page 1 of 54

EU Protocol Details in Accordance with CHMP Guidance for the Format and Content of the Protocol of Non-interventional Post-Authorisation Safety Studies (PASS)

Title	Global Lomitapide Pregnancy Exposure Registry			
Protocol version identifier	Version 3.0			
Date of last version of protocol	21 Nov 2013			
EU PAS register number	ENCEPP/SDPP/5329			
Active substance	Lomitapide			
Medicinal product	Lojuxta [®]			
Product reference	H0002578			
Procedure number	EU: H/C002578/0000			
Marketing authorisation holder(s)	Aegerion Pharmaceuticals [name]			
Joint PASS No				
Research question and objectives	To evaluate the outcomes of pregnancy in women treated with lomitapide at any time within 30 days prior to first day of Last Menstrual Period (LMP) or during pregnancy. The outcomes of primary interest are major congenital anomalies.			
Country(-ies) of study	Patients will be enroled from (but not limited to) countries in North America and Europe			
Author	[name] VP Medical Affairs EMEA			
Marketing authorisation holder(s)	Aegerion Pharmaceuticals, Inc. [name], France			
MAH contact person	[name]			

Confidential Page 2 of 54

SPONSOR'S APPROVAL

This protocol has been approved by Aegerion Pharmaceuticals, Inc.

Sponsor's Signatory: **[name], MD**

Vice President, Medical Affairs, EMEA

Signature: [name] Date: 27-1L November 2013

Confidential Page 3 of 54

INVESTIGTOR AGREEMENT

I have read this Aegerion Pharmaceuticals, Inc. Protocol No. AEGR-733-027:

Global Lomitapide Pregnancy Exposure Registry

I have fully discussed the objectives of this trial and the contents of this protocol with the Sponsor's representatives.

2. LIST OF ABBREVIATIONS

Abbreviation	Definition
AE(s)	Adverse Event(s)
CC	Coordinating Centre
CDC	Centers for Disease Control and Prevention
CRFs	Case Report Forms
eCRFs	Electronic Case Report Forms
EDC	Electronic Data Capture
EDD	Estimated Date of Delivery
EU	European Union
FDA	Food and Drug Administration
НСР	Healthcare Provider
HIPAA	Health Insurance Portability and Accountability Act
НоГН	Homozygous Familial Hypercholesterolaemia
ICBDM	International Clearinghouse for Birth Defects Monitoring
ICH	International Conference on Harmonization
IEC	Independent Ethics Committee
IRB	Institutional Review Board

Confidential Page 9 of 54

Abbreviation Definition		
LDL-C	Low Density Lipoprotein-Cholesterol	
LDL-R	Low Density Lipoprotein- Receptor	
LMP	Last Menstrual Period	
MACDP	Metropolitan Atlanta Congenital Defects Program	
MTP	Microsomal Triglyceride Transfer Protein	
NOAEL	No-observed-adverse-effect level	
PER	Pregnancy Exposure Registry	
PI	Package Insert	
PK	Pharmacokinetic	
PRCA	Pregnancy Root Cause Analysis	
REMS	Risk Evaluation and Mitigation Strategy	
RMP	Risk Minimization Plan	
SAE	Serious Adverse Event	
SAP	Statistical Analysis Plan	
SPC	Summary of Product Characteristics	
SOPs	Standard Operating Procedures	
SUSAR	Suspected Unexpected Serious Adverse Reaction	
UK	United Kingdom	

Confidential Page 10 of 54

Abbreviation	Definition
ULN	Upper Limit of Normal
US	United States
USPI	United States Prescribing Information

Confidential Page 11 of 54

4. ABSTRACT

4.1 Title

Global Lomitapide Pregnancy Exposure Registry version 2.0, 19Aug2013.

4.2 Rationale and Background

Lomitapide, a microsomal triglyceride transfer protein (MTP) inhibitor, was approved as Juxtapid[®] in the United States on December 21, 2012 and was authorized as Lojuxta[®] in the European Union on July 31, 2013. The approved indications in the two regions are quite similar and are described in Section 7. Homozygous Familial Hypercholesterolaemia (HoFH) is a serious, life-threatening disease caused by mutations in both alleles that encode the low density lipoprotein receptor (LDL-R), or proteins known to affect LDLR functionality. Subjects with HoFH typically have 4-10 fold elevations in LDL-C and develop premature atherosclerosis and coronary heart disease and can have cardiovascular events and complications such as myocardial infarction (MI) or aortic stenosis in the first decade of life. Untreated, subjects generally do not survive past age 30 (Raal, et al., 2011).

Due to its rarity and early mortality, the prevalence of HoFH is not well characterized. No studies accurately quantify the prevalence or incidence of the disease. The frequency of HoFH has been calculated to be 1 in 1 million in the general population based upon the estimated prevalence of the heterozygous state (1 in 500). In geographic regions with a presumed founder effect the prevalence has been observed to increase up to 10 in 1 million (Goldstein, et al., 1973; Goldstein, et al., 2001). A molecular diagnosis is not typically undertaken at the clinical practice level because, although over 1600 known mutations of the LDLR gene have been reported, unrecognized alleles lead to an inability to confirm the diagnosis and false negative reporting in 15-20% of cases (DeMott, et al., 2008; Varret, et al., 2007). In addition, genotyping is not widely available, is costly, may not be reimbursed, and does not influence treatment decisions. Consequently, HoFH is commonly diagnosed based on LDL-C levels, family history and clinical manifestations.

Women of reproductive age are among those affected by HoFH. Pregnancy is an event of special interest (ESI) in women exposed to lomitapide for 2 reasons. First, there are no reliable data on the use of lomitapide in pregnant women. Lomitapide may cause foetal harm when administered to a pregnant woman based on findings of teratogenicity in animal studies. Second, lomitapide may induce diarrhoea and vomiting due to its mechanism of action and decrease the

Confidential Page 13 of 54

absorption of oral contraceptives, thereby increasing the risk of unintended pregnancy. Lomitapide MTP inhibition causes triglyceride accumulation not only in the liver but also in the intestine. Presumably, diarrhoea develops as a consequence of this mechanism of action (Samaha et al., 2008). The reduced bowel transit time may affect the absorption of concomitant oral contraceptives.

The lomitapide US Prescribing Information (PI) and the EU Summary of Product Characteristics (SPC) include a contraindication for use during pregnancy and instructions that females of reproductive potential should have a negative pregnancy test before starting lomitapide and should use effective contraception during therapy with lomitapide.

The Global Lomitapide Pregnancy Exposure Registry (PER) will be conducted in all countries that are included in LOWER (Lomitapide Observational Worldwide Evaluation Registry) Protocol AEGR-733-025. Information on any spontaneous and literature reports of pregnancies with lomitapide exposure in patients who are not enrolled in LOWER or the PER will be added to the PER analyses once the pregnancies have been followed to outcome by the Aegerion Safety Department or its designee.

The PER will collect data on any pregnancies that occur in women exposed to lomitapide in the 30 days prior to conception or during pregnancy. Women residing in countries where the larger companion registry ("LOWER", protocol AEGR-733-025) is being offered who become pregnant will be offered to enrol into this PER and will be followed to pregnancy outcome. Due to the rarity of HoFH and the contraindications for lomitapide use during pregnancy, it is anticipated that the PER will collect a small number of pregnancies. All eligible pregnancies will be accepted; the pregnancies that are recorded in and reported from the PER will provide valuable information on birth outcomes following exposure to lomitapide. While the outcomes of primary interest are major congenital anomalies, full descriptions of all pregnancies and birth outcomes will be provided in the planned annual reports.

4.3 Research Question and Objectives

To evaluate the outcomes of pregnancy in women treated with lomitapide at any time within 30 days prior to the first day of Last Menstrual Period (LMP) or during pregnancy. The outcomes of primary interest are major congenital anomalies.

Confidential Page 14 of 54

4.4 Study Design

This is a global, longitudinal, observational study. Data will be collected at enrolment and periodically during pregnancy from prescribers, gynaecologists, paediatricians and other Health Care Providers (HCPs) who may be caring for the patient during the pregnancy or caring for the child. HCPs will be contacted during the pregnancy (each trimester), within 4 weeks after the estimated delivery date (EDD), and for paediatric follow-up at 12 weeks of age and at 12 months of age. In the US and in other countries where patient contact is possible, data will also be collected directly from patients during each trimester, at the EDD, and, for paediatric patients, at 12 weeks and 12 months.

Primary data collection will be completed using electronic case report forms (eCRFs) completed by the PER Coordinating Centre (CC) personnel. Medical records will be requested for all pregnancy outcomes and birth defects. Pregnancy outcomes and birth defects will be verified, whenever possible, by review of medical records.

4.5 Population

Patients to be enrolled in the PER include:

- Pregnant females:
 - exposed to lomitapide at any time within 30 days prior to first day of the LMP or during pregnancy.
 - willing to provide written informed consent and release medical records.

4.6 Variables

Data will be captured on eCRFs. Information included in the patient's medical record will be collected by the PER to verify the data provided by the patient and the HCP(s). The primary outcomes of interest are major congenital anomalies. Additionally, the following pregnancy outcomes will be captured and reported: live birth; spontaneous abortion/miscarriage; induced abortion; and foetal death/ stillbirth.

4.7 Data Sources

The PER CC will conduct outreach (further described in Section 9.3.4.1.1) to identify women who have become pregnant while being treated with lomitapide. Eligible patients will be enrolled in the study through the CC by their treating physician and followed through pregnancy

Confidential Page 15 of 54

outcomes and the final assessment (such as the evaluation of the infant if a live birth). In the US and other countries where it is permissible, patients may also self-enrol.

Data concerning patient history, pregnancy outcomes, and infant assessment will be collected at the indicated time points (enrolment, per trimester, prenatal follow-up, pregnancy outcome, and infant follow-up –up to 12 months) and entered into the PER Electronic Data Capture (EDC) system by CC personnel.

4.8 Study Size

The PER will collect lomitapide-exposed prospectively reported pregnancies and will also include retrospective reports of exposed pregnancies while the main registry ("LOWER", Protocol AEGR-733-025) remains open in the US. Additionally, reports of pregnancy and birth defects from post-marketing adverse event reports (spontaneous reports) and from published medical literature will be summarized within the annual PER study reports.

4.9 Data Analysis

A formal statistical analysis plan (SAP) will include details of all planned analyses and presentation of PER data. Since this is an observational study, descriptive analyses will be provided. Descriptive statistics will comprise the number of observations (n), mean, standard deviation (SD), median, minimum, and maximum for continuous variables; and n and percent for categorical variables. Data will be presented for all patients enrolled in the PER. An analysis of all PER participants combined will be provided. Separate analyses will also be conducted for prospective and retrospective reports. All data will be pooled for an additional analysis that includes spontaneous and literature reports from patients not participating in the PER. The proportion of pregnancies and births that have been lost to follow-up will also be calculated and reported. The primary outcome is major congenital abnormalities.

5. AMENDMENTS AND UPDATES

None

Confidential Page 16 of 54

6. MILESTONES

MILESTONE	PLANNED DATE		
Start of data collection	At time of first reported pregnancy after opening of the Lomitapide Observational Worldwide Evaluation Registry (LOWER)		
End of data collection	EU: Open Non-EU: At the closure of LOWER, which is planned for 01 March 2028 Note: any pregnancies that are on-going at the time of registry closure will be followed to outcome, with live births followed for an additional 12 months. Ongoing infant follow-up will be completed as well.		
Annual reports	Annually during the life of the PER		
Registration in the EU PAS register	To Be Determined		
Final report of study results	EU: Open Non-EU: 6 months after database lock (no later than 01 September 2028)		

Confidential Page 17 of 54

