9.3.4.2 PER Contact Schedule

In countries that allow contact with the patient and the HCP, during the course of the pregnancy the CC will contact the patient once per trimester. In countries with contact restricted to HCPs, during the course of the pregnancy the CC will contact the patient's HCP once per trimester.

Regardless of country of origin of the report, the patient's HCPs will be contacted at 6 to 7 months of gestation for the Prenatal Follow-Up and within 4 weeks after the EDD for Pregnancy Outcome Follow-Up. The infant's HCP will be contacted by the enroling HCP or by the CC when the infant is 12 weeks of age and at 12 months of age for paediatric follow-up.

The data collection schedule is outlined in Table 1 and Table 2.

Confidential Page 26 of 54

Table 1: Data Collection Schedule in Countries with Data Collection Restricted to HCPs

DATA COLLECTION	REGISTRATION BY LOMITAPIDE PRESCRIBER WITH CC	CC CONTACT WITH THE HCP AT EACH TRIMESTER	6 TO 7 MONTHS OF GESTATION FOR THE PRENATAL FOLLOW- UP	CC CONTACT WITH PRACTITIONER(S) AT THE PREGNANCY OUTCOME FOLLOW- UP WITHIN 4 WEEKS AFTER THE EDD	HCP OR CC CONTACT WITH THE INFANT'S HCP AT THE PAEDIATRIC FOLLOW-UP AT 12 WEEKS OLD AND 12 MONTHS OLD ¹
Consent	X				
Patient Demographics and Pregnancy History	X				
Lomitapide Use	X	X	X	X	X (if mother is nursing)
Concomitant Medications	X	X	X	X	X
Medical History	X				
Pregnancy Outcome				X	
Paediatric History and Examinations				X	X
Serious Adverse Events (Pregnancy-Related)		X	X	X	X

¹ The 12-week follow up should be conducted +/- one week.

Confidential Page 27 of 54

Table 2: Data Collection Schedule in Countries with Data Collection from Patients or HCPs

DATA COLLECTION	REGISTRATION/ ENROLMENT	CC CONTACT WITH THE PATIENT AT EACH TRIMESTER	CC CONTACT WITH THE PATIENT'S HCP(S) AT THE PRENATAL FOLLOW- UP, 6 TO 7 MONTHS OF GESTATION	CC CONTACT WITH THE HCP(S) AT THE PREGNANCY OUTCOME FOLLOW- UP ¹ WITHIN 4 WEEKS AFTER THE EDD	CC CONTACT WITH THE INFANT'S HCP AT THE PAEDIATRIC FOLLOW-UP AT 12 WEEKS AND 12 MONTHS OLD ^{2,3}
Consent ⁴	X				
Patient Demographics and Pregnancy History	X				
Contact Information	X	X	X		
Lomitapide Use	X	X	X	X	X (if mother is nursing)
Concomitant Medications	X	X	X	X	X
Medical History	X				
Pregnancy Status/ Outcome		X	X	X	
Paediatric History and Examinations				X	X
Serious Adverse Events (Pregnancy Related)		X	X	X	X

Confidential Page 28 of 54

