12. PLANS FOR DISSEMINATING AND COMMUNICATING STUDY RESULTS

12.1 Reporting to Regulatory Agencies

Interim reports will be submitted to the regulatory authorities, as required, based on agreed upon timelines. A final report will be submitted to the regulatory authorities within 6 months after database lock.

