2.2.5 Co-morbidity?				
2.2.6 Seasonality?				
2.3 Does the protocol define how the study population will be sampled from the source population? (e.g. event or inclusion/exclusion criteria)				21

Comments: There are broad eligibility criteria solely based on pregnancy status and treatment with lomitapide. The PER will remain open indefinitely in the EU; in non-EU countries the PER will close to enrolment when the LOWER closes.

Confidential Page 47 of 54

Section 3: Study design	Yes	No	N/A	Page Number(s)
3.1 Does the protocol specify the primary and secondary (if applicable) endpoint(s) to be investigated?				22-24
3.2 Is the study design described? (e.g. cohort, case-control, randomised controlled trial, new or alternative design)	\boxtimes			20
3.3 Does the protocol describe the measure(s) of effect? (e.g. relative risk, odds ratio, deaths per 1000 person-years, absolute risk, excess risk, incidence rate ratio, hazard ratio, number needed to harm (NNH) per year)				
3.4 Is sample size considered?			\boxtimes	
3.5 Is statistical power calculated?			\boxtimes	
Comments: A separate Statistical Analysis Plan will be prepared. All reported eligible pregnancies will be collected.				

Section 4: Data sources	Yes	No	N/A	Page Number(s)
4.1 Does the protocol describe the data source(s) used in the study for the ascertainment of:				
4.1.1 Exposure? (e.g. pharmacy dispensing, general practice prescribing, claims data, self-report, face-to-face interview, etc)				29-32
4.1.2 Endpoints? (e.g. clinical records, laboratory markers or values, claims data, self report, patient interview including scales and questionnaires, vital statistics, etc)				29-32
4.1.3 Covariates?				29-32
4.2 Does the protocol describe the information available from the data source(s) on:				

Confidential Page 48 of 54

Section 4: Data sources	Yes	No	N/A	Page Number(s)
4.2.1 Exposure? (e.g. date of dispensing, drug quantity, dose, number of days of supply prescription, daily dosage, prescriber)	\boxtimes			29-32
4.2.2 Endpoints? (e.g. date of occurrence, multiple event, severity measures related to event)				29-32
4.2.3 Covariates? (E.g. age, sex, clinical and drug use history, co-morbidity, co-medications, life style, etc.)				29-32
4.3 Is the coding system described for:				

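### The non-EU final-report limit of 01 September 2028 leaves no room for the follow-up after closure that the same milestone table promises

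*Protocol*

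**What the plan says.** The milestone table in Section 6 of the protocol makes three statements about the non-EU part of the registry.

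- End of data collection: "Non-EU: At the closure of LOWER, which is planned for 01 March 2028".
- A note in the same row: "any pregnancies that are on-going at the time of registry closure will be followed to outcome, with live births followed for an additional 12 months". It adds: "Ongoing infant follow-up will be completed as well".
- Final report: "6 months after database lock (no later than 01 September 2028".

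For the EU, both the end of data collection and the final report are entered as open.

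Section 12.1 repeats the reporting interval without the calendar limit: "A final report will be submitted to the regulatory authorities within 6 months after database lock". Section 9.3.4.2 places the infant contacts "when the infant is 12 weeks of age and at 12 months of age for paediatric follow-up". A comment in the Annex 2 checklist says that "in non-EU countries the PER will close to enrolment when the LOWER closes", so pregnancies can be enrolled up to the closure date.

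**The concern.** The note and the report date sit in one table and pull apart. The note extends non-EU follow-up well beyond closure, while the report date allows for none of it.

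The stake is the primary outcome, major congenital anomalies. The 12-month contact is the last scheduled look at the infant, and Section 9.4 lists among its data the anomalies found since the initial report, with age at diagnosis. Section 9.7.2 divides birth defects by live births. An infant born before lock but not yet followed to 12 months therefore counts in the denominator, while a defect found later does not reach the numerator. With that denominator fixed, the omission can only lower the rate, which is the unfavourable direction for a teratogenicity registry. Pregnancies undelivered at lock would be left out of the final report altogether. If follow-up is honoured instead, a stated milestone is missed.

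**Working it through.** **Inputs.** From Section 6: closure C = 01 March 2028; report limit L = 01 September 2028; infant follow-up of 12 months after live birth. From Sections 6 and 12.1: up to 6 months from lock to report. Assumptions not in the protocol: a 40-week term, and gestational age at closure, shown from 40 down to 4 weeks.

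**Reproducing the stated date.** C + 6 months = 01 September 2028 = L. Equivalently, L − 6 months = 01 March 2028 = C. The limit fits a 6-month reporting period only if lock falls on closure day.

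**What a closure-day lock would contain.** For 12-month follow-up to be complete at lock, the last birth must be by C − 12 months = 01 March 2027. For it to be complete by the report limit itself, the last birth must be by L − 12 months = 01 September 2027.

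**Pregnancies ongoing at closure that end in live birth.** Birth is on or after C, so follow-up ends on or after C + 12 months = 01 March 2029, which is 6 months after L. This bound needs no assumption about term or accrual. For the range:

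- birth = C + (40 − gestational weeks at closure) weeks
- end of follow-up = birth + 12 months
- report = end of follow-up + 6 months

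| Gestation at closure | Birth | Follow-up ends | Report at lock + 6 months | Months past L |
|---|---|---|---|---|
| 40 weeks | 01 Mar 2028 | 01 Mar 2029 | 01 Sep 2029 | 12.0 |
| 28 weeks | 24 May 2028 | 24 May 2029 | 24 Nov 2029 | 14.8 |
| 12 weeks | 13 Sep 2028 | 13 Sep 2029 | 13 Mar 2030 | 18.3 |
| 4 weeks | 08 Nov 2028 | 08 Nov 2029 | 08 May 2030 | 20.2 |

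**Infants already born at closure.** An infant aged *a* months at closure reaches 12 months at C + (12 − *a*) months.

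- *a* = 3: 01 December 2028, after L.
- *a* = 6: 01 September 2028, exactly L.
- *a* = 9: 01 June 2028, before L. A full 6 months for reporting would run to 01 December 2028, but Section 12.1 sets 6 months as a maximum, so a faster report could still meet L.

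Infants under 6 months old at closure therefore also finish after the limit, however fast the report is written.

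**The case against.** The strongest reply is that the collision is conditional. It needs a non-EU pregnancy ongoing at closure that ends in live birth, or a non-EU infant too young to finish follow-up in time. Sections 4.2 and 7 expect few pregnancies, and Section 9.5 says the number cannot be accurately estimated, so there may be none. A pregnancy that ends in early loss could be reported in time. This stands as a limit on scope. It does not remove the conflict, because both the promise and the latest date are unconditional.

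A second reply is that later non-EU data could appear in the annual reports. Section 6 has these continue for the life of the registry, and the EU part stays open. That is possible, but nothing in the protocol assigns post-closure non-EU data to them, provides a supplementary non-EU report, or describes a lock before follow-up ends.

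Some stronger readings are tempting and are not supported:

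- A reader might infer that undelivered pregnancies enter the final rate without an outcome and bias it. Section 9.7.2 uses live births as the denominator, so they are outside the rate. The downward effect comes only from live-born infants with shortened follow-up, and the outcome and 12-week contacts, where completed, narrow it.
- A reader might put a percentage on the pregnancies affected. That needs a start date and an accrual pattern. Section 6 starts collection at the first reported pregnancy, and no accrual figure is given.
- A reader might add that Section 4.8, which refers to LOWER while it "remains open in the US", conflicts with the open EU period. That phrase may qualify only the retrospective reports, so it is too ambiguous to support the point.

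**Conclusion.** The milestone table is wrong as written for the non-EU report. The limit of 01 September 2028 is closure plus 6 months and allows nothing for the follow-up promised in the same table. For any live birth from a pregnancy ongoing at closure, follow-up ends at least 6 months after the limit. A report 6 months after a complete-data lock falls 12 to 20 months after it, between about September 2029 and May 2030. The lower figure is birth on closure day; the upper figure rests on a 40-week term and enrolment at about 4 weeks' gestation at closure.

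The EU entries are open and are not affected. How many pregnancies or infants would be caught, and hence how far the rate would move, cannot be derived from the protocol. In a registry this small, one late-diagnosed defect could change the rate materially.

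**What to change.** Define the non-EU database lock in Section 6 as completion of the last promised 12-month infant follow-up among pregnancies enrolled by LOWER closure. Set the final report at 6 months after that lock. Delete the 01 September 2028 limit or replace it with a date of about mid-2030. A rule tied to closure is safer than a fixed date, since closure itself is only planned.

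Alternatively, keep the September 2028 report, label it interim on data to closure, and commit to a final non-EU report once follow-up is complete.

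Either route needs a protocol amendment with whatever regulatory and IRB/IEC approval Section 9.9.2.2 requires, and a later final-report milestone. It adds no patients and no procedures, because the follow-up is already promised.
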